6.10.3.1.5. SARS-CoV-2 Clearance

See Section 6.10 for more details on the definition of viral clearance.

The proportion of participants that achieve SARS-CoV-2 clearance at Days 3, 5, 7, 11, and 29 will be summarized by treatment in frequency tables and listed.

In addition, the number of participants that achieve SARS-CoV-2 clearance at Days 3, 5, 7, 11, and 29 will be analyzed using logistic regression to compare active treatment versus placebo at each dose level.

6.10.3.1.6. Time to SARS-CoV-2 Clearance

See Section 6.10 for more details on the definition of viral clearance and date of viral clearance.

Time to SARS-CoV-2 clearance is defined (in days) as:

(Date when SARS-CoV-2 clearance status is first changed to "Yes" – Infusion Date + 1)

If a patient has not experienced SARS-CoV-2 clearance by completion or early discontinuation of study/study treatment and assessment period, the patient will be censored at the date of their last visit during the treatment and assessment period.

Time to SARS-CoV-2 clearance will be evaluated during the study treatment and assessment period only, and will be summarized by treatment and listed. Cox proportional hazard model will be used.

Time to SARS-CoV-2 clearance will be presented graphically.

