6.1.1 Analysis Populations	Added analyses for Treatment	Protocol revision (c)
	Arms 7-8	, ,
	Added a per-protocol population	Additional sensitivity analyses
6.7 Participant Characteristics	Added analyses for females who	Protocol revision (c)
	are pregnant at baseline	
6.10.3.4 SARS-CoV-2 Clearance	Removed Day 22 analyses	Do not collect NP swabs on Day 22
6.10.3.6.1 Symptom Resolution	Added analyses for day 22 and	Protocol revision (b)
	29 for proportion of patients that	
	achieve symptom resolution	
6.10.3.6.5 Symptom Improvement	Added analyses for day 22 and	Protocol revision (b)
	29 for proportion of patients that	
	achieve symptom resolution	
6.10.3.7 COVID-19-Related	Clarified that Death is Death	Clarification
Hospitalization or Death From Any	from all causes	
Cause	Clarify 1 day Day 4 is Day 4	Clariff and an
6.10.3.7.1 Bayesian Modeling for COVID-19-Related Hospitalization	Clarified that Death is Death from all causes	Clarification
or Death From Any Cause	Holli all Causes	
6.10.3.8 COVID-19-Related	Clarified that Death is Death	Clarification
Hospitalization, Emergency Room	from all causes	Charication
Visit, or Death From Any Cause		
6.12.9 Immunogenicity	Added analyses for VIR-7831	Protocol revision (c)
6.13 Subgroup Analyses	Added subgroup analyses for	Protocol revision (c)
	females who are pregnant at	
	baseline	
6.15.1 Interim Analyses	Added potential interim analysis	Protocol revision (c)
	for Treatment Arms 7-8	
	Added analyses for primary	Clarification
	outcome	

CCI

Overall Rationale for Version 6:

Section # and Name	Description of Change	Brief Rationale
6.1 General Considerations	Removed analyses for female participants who are pregnant at	Protocol revision (d)
	baseline	
6.7 Participant Characteristics	Removed summary for female participants who are pregnant at baseline	Protocol revision (d)
6.10.3.6.2 Time to Symptom Resolution	Added a sentence that states patients will be censored at the date of hospitalization	Clarification
6.10.3.6.6. Time to Symptom Improvement	Added a sentence that states patients will be censored at the date of hospitalization	Clarification
6.13 Subgroup Analyses	Removed analyses for female participants who are pregnant at baseline	Protocol revision (d)

Overall Rationale for Version 7:

Section # and Name	Description of Change	Brief Rationale
6.3.4. Last Observation Carried	Added section for missing data	Added LOCF imputation method for the

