5.1.4. Posttreatment Follow-up

Posttreatment follow-up assessments will be conducted at Day 60 and Day 85 to assess clinical status and for adverse events. Strategies to manage infection risks and reduce the burden of return visits may be used by sites, such as home visits.

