6.1.3. Study Time Intervals

To calculate the length of any time interval or time period in this study, the following formula will be used:

 $Length\ of\ interval\ (days) = End\ Date - Interval\ Start\ Date + 1$

To convert any time length from days to weeks, the following formula will be used:

Length of interval (weeks) = Length of interval (days)/7

Only for the purpose of calculating the length of study period time intervals, the words "prior to" in Table PYAH.6.2 should be understood to mean "the day before" while the words "after" should be understood to mean "the day after." For the purpose of determining whether a date/time lies within an interval, these words are intended to convey whether the start or end of the period is inclusive of the specified date.

Study Period	Interval Start Definition	Interval End Definition
Screening: All participants who sign informed consent are considered as entering the Screening Period.	Informed consent date	Prior to the start of Treatment and Assessment Period.
Treatment and Assessment Period: All participants who are randomized to the study are considered as entering the treatment and assessment period.	At the start of study drug administration date/time following randomization. For participants who are randomized but not dosed, the treatment and assessment period starts on the date of randomization.	The minimum of treatment and assessment period discontinued date, study discontinuation date, or first post treatment follow-up visit date.
Post-Treatment Follow-Up: All participants who had a follow up visit are considered as entering follow-up period.	After the Treatment and Assessment Period ends.	The maximum of the last study visit date or study disposition date.

Table PYAH.6.2. Definition of Study Period Time Intervals

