6.10. Efficacy Analyses

The analysis of the viral load lab results will utilize the following conventions:

For qualitative endpoints in the trial (viral clearance yes/no, time to viral clearance) the lab determination of "positive"/"negative" will be used. SARS-CoV-2 clearance (yes/no) is defined as 2 consecutive negative tests for the SARS-CoV-2 virus. The date of viral clearance is defined as the earliest date of the 2 consecutive negative tests.

For quantitative endpoints in the trial (change from baseline, area under the response viral load curve [AUC]), the viral load will be derived based on cycle threshold (Ct) values with the following considerations:

- Two Ct values will be provided on 2 different genes: N1 and N2. N1 will be used as the primary measure; N2 will only be used when the Ct value for N1 is not available.
- Ct values range between 0 and 45.
- Negative CoV-2 tests will be associated with a Ct value of 45.
- For any sample with a positive CoV-2 test result, an additional normalization step will be taken in the analysis. The viral load Ct value described in the previous steps

will be subtracted by (RP Ct -26.17), where RP Ct is a measure for the amount of material in the sample, and 26.17 is a historical average value of RP Ct for this assay, used here to center the RP Ct values. This step will be skipped if a valid RP Ct value is unavailable for the sample.

• The (log base 10) viral load will be calculated from the Ct value (45-Ct)/log₂10, or (45-Ct)/3.321928.

A lower Ct value of 40 for negative CoV-2 tests may be explored as part of exploratory PK/PD exposure-response analysis (Section 6.11).

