6.10.3.2. Symptom Questionnaire

Participants will rate their overall clinical status and severity of symptoms associated with COVID-19 by a daily questionnaire up to Day 11 and on Days 22 and 29. See Appendix 1 for further details regarding the symptoms and overall clinical status participant questionnaire.

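### Time to SARS-CoV-2 clearance is censored at the last visit, so participants who stop giving swabs before Day 11 but keep attending stay in the risk set unassessed

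*SAP*

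**What the plan says.** Section 6.10 defines the event: "SARS-CoV-2 clearance (yes/no) is defined as 2 consecutive negative tests for the SARS-CoV-2 virus". It also dates it: "The date of viral clearance is defined as the earliest date of the 2 consecutive negative tests". Section 6.10.3.1.5 gives the assessment days: "The proportion of participants that achieve SARS-CoV-2 clearance at Days 3, 5, 7, 11, and 29 will be summarized by treatment".

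For a participant who never clears, section 6.10.3.1.6 states that "the patient will be censored at the date of their last visit during the treatment and assessment period". No swab or test result is needed at that visit. A Cox model is then used.

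Table PYAH.6.2 in section 6.1.3 ends the period at: "The minimum of treatment and assessment period discontinued date, study discontinuation date, or first post treatment follow-up visit date". Section 5.1.4 places the follow-up visits: "Posttreatment follow-up assessments will be conducted at Day 60 and Day 85". None of these dates depends on a swab.

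Contacts without a swab exist. Section 6.10.3.2 has symptoms rated "by a daily questionnaire up to Day 11 and on Days 22 and 29", and section 6.10.3.2.1 allows collection by telephone. The Version 5 entry in section 3 (Revision History) gives as a reason "Do not collect NP swabs on Day 22", and the current list of clearance days also omits Day 22.

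The missing-swab rule in section 6.3.1 (modified non-responder imputation) is stated for the yes/no clearance endpoint. No missing-swab rule is stated for the time-to-event endpoint.

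**The concern.** Censoring at a given date asserts that the participant was observed and event-free up to that date. Here that is true only while swabs are being taken. Someone whose last swab is on Day 3, and who then only attends visits or answers the questionnaire, cannot have an event on Day 5, 7 or 11. Under the rule this person is still in the denominator on each of those days.

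The estimated clearance curve is then too low in any arm with early swab stoppers. The hazard ratio for Arms 1-11 depends on how many participants in each arm stop swabs, as well as on how fast the virus clears. The direction of the error is not fixed in advance, so the rule cannot be defended as conservative.

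**Working it through.** The SAP gives no event count, power or drop-out figure for this endpoint, so there is no figure to reproduce. The check has three steps.

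**1. Who is affected.** With swabs on Days 3, 5, 7, 11 and 29, the possible consecutive pairs are (3,5), (5,7), (7,11) and (11,29). The event takes the first date, so scheduled events can fall only on Days 3, 5, 7 and 11. A participant swabbed through Day 11 is at risk on Day 11 whether censored at the last swab or at a later visit on Day 22, Day 29 or beyond. Moving from last visit to last swab therefore matters only for those who stop swabs before Day 11.

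**2. Closed-form check of the Day 11 curve.** Assumptions, none of them in the SAP:
- Clearance time is 1 + a Weibull variable with shape 1.3 and scale 10 days, and a participant who clears stays negative.
- A share s of participants stop swabs, unrelated to clearance. Half stop after Day 3 and half after Day 5, and all attend to Day 29.

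F(t) = 1 − exp(−((t−1)/10)^1.3), so F(11) = 1 − exp(−1) = 0.632 and F(3) = 1 − exp(−0.1234) = 0.116.

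Under last-visit censoring nobody leaves the risk set before Day 29, so the Kaplan-Meier estimate at Day 11 is the raw proportion with an event. Day 3 stoppers can never have an event. Day 5 stoppers can have one only if they cleared by Day 3. Hence:

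estimate = (1 − s) × 0.632 + s × 0.5 × 0.116

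shortfall = s × (0.632 − 0.058) = 0.574 s

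For s = 5%, 10% and 20% the shortfall is 2.87, 5.74 and 11.48 percentage points, giving estimates of 60.3%, 57.5% and 51.7% against a true 63.2%.

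**3. Simulation of the hazard ratio.** The same assumptions were used with 20,000 per arm, the two-negative rule, swabs on Days 3, 5, 7, 11 and 29, and a Cox model with Efron ties. The last column censors at the last swab that still had a later swab to confirm it.

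| True HR | Stop early, placebo / active | Last visit | Last swab | Last confirmable swab |
|---|---|---|---|---|
| 1.5 | 0% / 0% | 1.487 | 1.487 | 1.487 |
| 1.5 | 5% / 5% | 1.460 | 1.484 | 1.485 |
| 1.5 | 10% / 10% | 1.436 | 1.479 | 1.480 |
| 1.5 | 20% / 20% | 1.414 | 1.490 | 1.492 |
| 1.0 | 15% / 5% | 1.158 | 1.027 | 1.001 |
| 1.0 | 20% / 10% | 1.162 | 1.039 | 1.013 |
| 1.0 | 5% / 15% | 0.865 | 0.974 | 0.999 |

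Each row applies the three rules to the same simulated participants, so the columns should be compared within a row. The simulated Day 11 clearance in the placebo arm under equal stopping (true HR 1.5) was 60.5%, 57.6% and 51.6% with last visit, against 63.3%, 63.3% and 63.0% with the last confirmable swab. This agrees with step 2. With no early stopping the three rules coincide, which isolates the censoring date as the cause.

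**The case against.** The strongest reply is about size. Arms 1-11 are double-blind, nothing in the SAP suggests that swab refusal differs by arm, and the share who stop swabs but keep attending is unknown. With equal stopping of 5% the hazard ratio moves only from 1.48 to 1.46. Even the imbalanced case is modest against sampling error. With 100 per arm and 15% / 5% stopping, events number about 100 × 0.548 + 100 × 0.605 = 115. The standard error of the log hazard ratio is then about 2/√115 = 0.19, and the bias is log 1.158 = 0.147, under one standard error. All of this stands, and it limits the weight of the point. It does not make the rule correct: a bias does not shrink as numbers grow, and the Kaplan-Meier curve is lowered even when stopping is equal.

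A second reply is that last-visit censoring matches the non-responder convention of section 6.3.1. That section names only the yes/no analysis. If it were extended here, a missing swab without earlier clearance would become a No, which is the same unobserved non-event.

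A reader might also infer that nearly every uncleared participant is mishandled, because the period can run to the Day 60 visit and Day 22 has no swab. The documents do not support this. The last scheduled event date is Day 11, so those contacts, or missing only the Day 29 swab, change no scheduled risk set when the last visit is compared with the last swab. Nor are such participants recorded as known to be infected: their status is no confirmed clearance.

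**Conclusion.** The point holds in a limited form. As written, the rule keeps participants who stop swabs before Day 11 at risk on days when the event could not be observed. On the assumed inputs, equal stopping of 5% to 20% lowers Day 11 clearance by about 3 to 11 percentage points and pulls a true hazard ratio of 1.5 down to between 1.46 and 1.41. A 10-point imbalance with no true effect gives about 1.16 or 0.86.

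These figures depend on the assumed clearance distribution, on stopping after Day 3 or 5 being unrelated to clearance, and on stopping shares that the SAP does not give. If few participants stop early the effect is close to zero. The swab days are taken from the list of clearance days.

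The hazard-ratio concern applies to Arms 1-11. Section 6.1.4 makes Arms 12-14 descriptive only, so there it touches only a clearance curve, if one is drawn. Section 6.5 applies no multiplicity control to secondary endpoints. The change is worth making because it is cheap, but the SAP does not show that any result would be materially altered.

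**What to change.** In section 6.10.3.1.6, replace the last-visit date. Censor a participant without confirmed clearance at the date of the last valid RT-PCR swab that was followed by a later valid swab in the treatment and assessment period, or at Day 1 if there is none.

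Censoring simply at the last swab would remove most of the bias but not all of it, because a first negative on the final swab can never be confirmed. In the table it leaves hazard ratios of about 1.04 and 0.97 under no effect, against about 1.00 with the proposed rule.

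The cost is one phrase and one programming line, and some participants contribute less follow-up time. In particular, a participant swabbed through Day 11 without a Day 29 swab would be censored at Day 7, because a first negative on Day 11 could not be confirmed. The simulation does not include such participants, so the number affected should be reported.

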6.10.3.2. Symptom Questionnaire

Participants will rate their overall clinical status and severity of symptoms associated with COVID-19 by a daily questionnaire up to Day 11 and on Days 22 and 29. See Appendix 1 for further details regarding the symptoms and overall clinical status participant questionnaire.

6.10.3.2.1. Symptom Resolution

For treatment groups 1-8, symptom resolution is defined as all symptoms (those scored 0 to 3) on the symptom questionnaire scored as absent.

For treatment groups 9-14, symptom resolution is defined as a score of 0 for shortness of breath, feeling feverish, body aches and pains, sore throat, chills, and headache, and a score of 0 or 1 for cough and fatigue on the symptom questionnaire.

The proportion of participants that achieve symptom resolution at Days 3, 5, 7, 11, 22, and 29 will be summarized by treatment in frequency tables and listed.

In addition, the number of participants that achieve symptom resolution at Days 3, 5, 7, 11 22, and 29 will be analyzed using logistic regression to compare active treatment versus placebo at each dose level.

Symptom questionnaire data may be collected either through direct data capture (by phone call or in person) or through a paper diary. Symptom resolution may also be analyzed by subgroups for modality.

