6.1.1. Analysis Populations

Patient populations are defined in Table PYAH.6.1 along with the analysis to be used to conduct. The treatment groups and inferential comparisons described in Table PYAH.6.1 will be used unless otherwise specified. Also, unless otherwise specified, for all populations/analysis, participants will be analyzed according to the treatment to which they were assigned.

Table PYAH.6.1. Analysis Populations

Population	Description
Entered	Definition: All participants who signed informed consent.
	Purpose: Used for disposition analysis.
	Treatment Groups: None
	Inferential Comparisons: None
Efficacy	Definition: All randomized participants who received study intervention and
	provided at least 1 postbaseline measure viral load measurement. Participants
	will be analyzed according to the intervention to which they were randomized
	(Intention to treat).
	Purpose: Used for efficacy and pharmacodynamic variables analyses.
	Treatment Groups (Short Label):
	Treatment Arms 1-6:
	175 mg LY3819253 and 350 mg LY3832479 (175/350 LY/LY2), 350
	mg LY3819253 and 700 mg LY3832479 (350/700 LY1/LY2), 700 mg
	LY3819253 and 1400 mg LY3832479 (700/1400 LY/LY2), 2800 mg
	LY3819253 and 2800 mg LY3832479 (2800/2800 LY/LY2), 700 mg
	LY3819253 (700 LY), and placebo (Pbo).
	Treatment Arms 7-8:
	700 mg LY3819253 and 500 mg VIR-7831 (700/500 LY/VIR), and
	placebo (Pbo).
	Treatment Arms 9-11:
	175 mg LY3853113 (175 LY3), 175 mg LY3853113 + 700 mg
	LY3819253 + 1400 mg LY3832479 (LY3/LY/LY2), placebo (Pbo)
	Treatment Arms 12-13:
	175 mg LY3853113 (175 LY3) and 175 mg LY3853113 + 700 mg
	LY3819253 + 1400 mg LY3832479 (LY3/LY/LY2)
	Treatment Arm 14:
	175 mg LY3853113 + 700 mg LY3819253 + 1400 mg LY3832479
	(LY3/LY/LY2)
	Additional optional combination arm may be added if decided.
	Inferential Comparisons:
	Treatment Arms 1-6:
	Each LY dose versus placebo
	Treatment Arms 7-8:
	700/500 LY/VIR dose versus placebo
	Treatment Arms 9-11:
	Each LY dose versus placebo
	Treatment Arms 12-14:
	None
Safety	Definition: All participants randomly assigned and who received any amount of
	study intervention. Participants will be analyzed according to the intervention
	they actually received.
	Purpose: Used for safety analyses, analyses of COVID-19-related
	hospitalization or death from any cause.
	Treatment Groups (Short Label):
	Treatment Arms 1-6:
	175 mg LY3819253 and 350 mg LY3832479 (175/350 LY/LY2), 350
	mg LY3819253 and 700 mg LY3832479 (350/700 LY1/LY2), 700 mg

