Treatment comparisons of continuous efficacy, and pharmacodynamic variables with multiple postbaseline measurements will be made using a mixed-effects model repeated measures (MMRM) analysis. When MMRM is used, it includes: (a) treatment group, (b) baseline value in the model, (c) visit, and (d) the interactions of treatment-by-visit as fixed factors. The covariance structure to model the within-patient errors will be unstructured. If the unstructured covariance matrix results in a lack of convergence, the heterogeneous Toeplitz covariance structure, followed by the heterogeneous autoregressive covariance structure, will be used. The first structure to yield convergence will be used for inference. The Kenward-Roger method will be used to estimate the denominator degrees of freedom. Type III sums of squares for the least-squares (LS) means will be used for the statistical comparison; the 95% confidence interval (CI) will also be reported. Unless otherwise specified, for MMRM, reported data from only planned visits will be used as the primary analysis.

Treatment comparisons of continuous efficacy, safety, and health outcome variables with a single postbaseline timepoint will be made using analysis of covariance (ANCOVA) with: (a) treatment group, and (b) baseline value in the model. Type III sums of squares for LS means will be used for statistical comparison between treatment groups. The LS mean difference, standard error, p-value, and 95% CI, unless otherwise specified, will also be reported. Missing data imputation method for the ANCOVA model is specified in Section 6.3.

Treatment comparisons for binary endpoints will be made using logistic regression with a Firth penalized likelihood (Firth 1993). The model will include the treatment groups. The Firth correction can be implemented in PROC Logistic by including 'firth' as an option in the model statement. The odds ratio and the corresponding CIs, as well as the treatment differences and the corresponding CIs, will be reported. If the number of observed events is less than 5 in any treatment arm an exact test (i.e., Fisher's exact) will be conducted instead of using a logistic regression.

The Kaplan-Meier (KM) product limit method will be used for time-to-event analyses. The hazard ratio and log-rank test will be reported. Time for all analyses will be described in units of days.

For all change from baseline analyses, patients who do not have a valid baseline measure will be excluded.

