6.3.6. Modified Last Observation Carried Forward

Analyses of symptom data, with the exception of change in symptom score, will utilize a modified last observation analysis (mLOCF). The mLOCF method is performed by carrying forward the last nonmissing postbaseline assessment to the subsequent missing assessments for analysis. For patients who die, all missing collection time points subsequent to the date of death will be imputed to Severe.

After mLOCF imputation, data from participants with nonmissing baseline and at least 1 postbaseline observation will be included in the analyses. The mLOCF imputation helps ensure that the maximum number of randomized participants who were assessed postbaseline will be included in the analyses and unfavorable terminal events are represented.

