6.10.3.2.2. Time to Symptom Resolution

Time to symptom resolution is defined (in days) as:

```
(First study day when symptom resolution status is changed to "Yes" – Infusion Date + 1)
```

If a patient has not experienced symptom resolution by completion or early discontinuation of study/study treatment, the patient will be censored at the date of their last visit during the treatment and assessment period. If a patient is hospitalized, the patient will be censored at the date of hospitalization.

Time to symptom resolution will be evaluated during the treatment and assessment period only and will be summarized by treatment and listed. Cox proportional hazard model will be used.

Time to symptom resolution will be presented graphically.

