6.10.3.2.3. Time to Sustained Symptom Resolution

For treatment groups 9-14, sustained symptom resolution is defined as 2 consecutive assessments with a score of 0 for shortness of breath, feeling feverish, body aches and pains, sore throat, chills, and headache; and a score of 0 or 1 for cough and fatigue on the symptom questionnaire. Time to sustained symptom resolution is defined (in days) as:

(First study day when sustained symptom resolution status is changed to "Yes" – Infusion Date + 1)

For Treatment Arms 9-11, similar methodology, as described in Section 6.10.3.2.2, will be utilized to perform treatment group comparisons.

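### The Arms 9-14 symptom resolution rule can already be met at baseline, and the SAP neither excludes nor handles participants who meet it

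*SAP*

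**What the plan says.** SAP section 6.10.3.2.1 has two definitions. For Arms 1-8, "symptom resolution is defined as all symptoms (those scored 0 to 3) on the symptom questionnaire scored as absent". For Arms 9-14, six of the eight scored symptoms must be 0, but the text ends "chills, and headache, and a score of 0 or 1 for cough and fatigue on the symptom questionnaire". Neither definition refers to the baseline score.

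Section 6.10.3.2.2 times the event from "First study day when symptom resolution status is changed to" Yes. Section 6.10.3.2.3 uses the same construction, and "sustained symptom resolution is defined as 2 consecutive assessments with a score of 0 for shortness of breath", with the same thresholds for the other symptoms.

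The provisions that decide who is analysed, and how, are these:

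- **Efficacy population (6.1.1):** "All randomized participants who received study intervention and" who have at least one post-baseline viral load. There is no symptom condition.
- **Imputation for symptom data (6.3.6):** "data from participants with nonmissing baseline and at least 1 postbaseline observation will be included in the analyses". There is no minimum baseline score.
- **Logistic model (6.1.4):** "The model will include the treatment groups". No baseline symptom term is named.
- **Baseline (6.1.2):** the last non-missing value on or before the date of dosing.

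By contrast, symptom improvement (6.10.3.2.6) is tied to baseline: a symptom that was mild at baseline has to become absent.

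**The concern.** Resolution is meant to record recovery. Under the Arms 9-14 rule, a participant who enters with cough scored 1, and perhaps loss of taste (a yes/no item outside the 0-3 scores), satisfies the definition before the infusion. If nothing changes, the SAP counts that person as resolved, yet not as improved.

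Three secondary endpoints are touched: the proportion resolved, time to resolution and time to sustained resolution. In Arms 9-11 such participants add responders to active and placebo alike, which shrinks the difference. In Arms 12-14 they raise a rate that has no comparator. For the time endpoints the SAP does not settle how they are coded, so two programmers could each follow the text and report different hazard ratios.

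**Working it through.** **1. Which baseline profiles meet the rule.** Eight symptoms scored 0 to 3 give 4^8 = 65,536 profiles. The Arms 9-14 rule fixes six at 0 and allows 0 or 1 on two, so 2 × 2 = 4 profiles satisfy it. One is symptom-free. The other three have mild cough, mild fatigue or both. If unchanged after baseline, all three count as resolved under 6.10.3.2.1 and fail the improvement rule in 6.10.3.2.6. None of the three would count as resolved under the Arms 1-8 rule, which can be met at baseline only by someone with every scored symptom absent.

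**2. Effect on the proportions, Arms 9-11.** The SAP gives no power figure for symptom resolution, so there is none to reproduce. Inputs:

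- n = 122 per arm (section 5.2).
- Two-sided alpha 0.05 (section 6.1.4).
- Illustrative resolution rates of 40% on placebo and 58% on active among participants who do not meet the rule at baseline (assumed).
- q, the share already meeting the rule, from 5% to 20% (assumed; not in the SAP).
- Participants already meeting the rule stay within it and show no treatment effect (assumed).

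All participants: each rate becomes q + (1 − q) × rate, so the difference is 18(1 − q) points with n = 122. Restricted: the difference stays at 18 points with n = 122(1 − q).

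Power = Φ[(d − 1.96 × SE0) / SE1], where SE0 is the pooled and SE1 the unpooled standard error. For q = 10%:

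- All participants: 46.0% versus 62.2%, d = 0.162, SE0 = 0.0638, SE1 = 0.0630, power 72.1%.
- Restricted: n = 109.8, d = 0.180, SE0 = 0.0675, SE1 = 0.0664, power 76.4%.

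| q | Difference, all (points) | Power, all | n per arm, restricted | Power, restricted |
|---|---|---|---|---|
| 0 | 18.0 | 80.7% | 122 | 80.7% |
| 5% | 17.1 | 76.5% | 115.9 | 78.6% |
| 10% | 16.2 | 72.1% | 109.8 | 76.4% |
| 20% | 14.4 | 63.0% | 97.6 | 71.4% |

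The fair comparison is along each row. Restriction recovers the 18-point difference but not the participants, so it cannot return power to 80.7%.

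**3. Effect of the undefined coding on the hazard ratio.** Assume exponential resolution times, placebo median 7 days, true hazard ratio 1.3 and daily assessment to Day 29. The expected share with an event on Day t is (1 − q)[exp(−λ(t − 2)) − exp(−λ(t − 1))], with λ = ln 2 / 7 on placebo and 1.3 times that on active. A Cox model fitted to these expected counts gives:

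- Already Yes counted as an event on Day 2: about 1.27 at q = 10% and 1.23 at 20%.
- Already Yes never changes and is censored at the end: about 1.20 and 1.16.
- Restricted: 1.30 at either share.

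Daily assessment is a simplification, because the questionnaire is daily only to Day 11. The point is the gap between the first two lines, which the SAP leaves to the programmer.

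**The case against.** **These participants can still respond to treatment.** A reader might infer that they count as resolved whatever they receive. That does not follow. Status is judged separately at each listed day, and someone whose cough rises to 2, or who becomes breathless, is not resolved that day. Treatment can act by preventing worsening. This objection stands, and the dilution figures depend on assuming otherwise.

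**Opposite classification is not established.** A reader might infer that the proportion and the time analysis must code the same person in opposite ways. Section 6.10.3.2.2 censors patients who have not experienced resolution, a description that hardly fits someone who meets the definition throughout. The text supports undefined, and no more than that.

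**The number affected is unknown.** Eligibility is in the protocol, which is not shown, and may keep q near zero. A population described as mild to moderate makes minimal symptoms plausible but does not size the group. This stands.

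**There is no false-positive bias.** Randomisation balances baseline status across Arms 9-11, so the effect is conservative. Arms 12-14 have no inferential comparison (6.1.1, 6.1.4), and secondary endpoints carry no multiplicity control (6.5). All of this stands.

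**Baseline is used elsewhere.** Improvement refers to it, and the change-score and symptom AUC models include it as a covariate. The revised Arms 9-14 definition was a deliberate Version 10 change. True, but neither fact tells anyone how to treat a participant who is already Yes at baseline on the resolution endpoints.

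**Conclusion.** The point holds in limited form. The Arms 9-14 definition can be met before dosing, and nothing in the SAP excludes or handles those who meet it. They count as resolved, with no change in symptoms, on any day their scores stay within the rule. Their coding in both time endpoints is undefined.

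In Arms 9-11 the consequence is dilution towards no difference; in Arms 12-14 it is a higher descriptive rate. On the illustrative 40% and 58%, restriction gains about 2 percentage points of power at q = 5% (78.6 − 76.5), 4 at 10% (76.4 − 72.1) and 8 at 20% (71.4 − 63.0). The gain is small at low q, and its size rests on three assumptions: the rates, q, and no treatment effect among those already meeting the rule. The definitional gap itself needs none of them. The change is a cheap improvement; no primary result is affected.

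**What to change.** In 6.10.3.2.1 to 6.10.3.2.3:

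- Base the resolution and sustained-resolution analyses on participants who do not meet the arm-specific definition at the last pre-dose questionnaire.
- Require a strictly pre-dose value. The 6.1.2 baseline admits any value on the dosing date, so a post-dose score could decide who is analysed. With a pre-dose value the randomised comparison is kept.
- Report the number excluded in each arm.
- Keep the all-participants analysis as a sensitivity analysis, with a stated rule for those already Yes at baseline: whether they are an event at the first post-baseline assessment or are censored and, for the sustained endpoint, whether the baseline assessment may be the first of the two.

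The cost is a baseline flag and a few sentences. The downsides are a smaller denominator, and that worsening among minimally symptomatic participants is seen only in the sensitivity analysis.
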